10.4.3. Exploratory Endpoint(s)

Plasma and CSF concentration levels of CY6463 will be summarized for the PK population at each nominal timepoint on scheduled study visits. Additionally, the following descriptive statistics will be presented: number and percentage of participants with values that are below the assay's limit of quantification; geometric mean; and coefficient of variation, calculated as $100 * SD / mean$. PK parameters, if available, will also be summarized using descriptive statistics for the PK population.

All other exploratory endpoints will be summarized by treatment group for each assessment timepoint using the ITT population. Baseline values used to calculate the change from baseline in these endpoints will be defined as the last non-missing assessment prior to the first administration of study drug, usually the predose assessment on Day 1.

Analyses of change from baseline exploratory endpoints will be conducted using the ITT population. A mixed-effect model repeated measures (MMRM) analysis with change from baseline as the response variable, treatment, visit, and treatment-by-visit interaction as fixed effects and the respective baseline value as the covariate with unstructured as the variance-covariance structure will be performed. Treatment differences between the CY6463 group and the placebo group will be estimated for the overall treatment period and at each assessment timepoint. Least square means and least square mean differences between the CY6463 group and placebo and their associated 90% confidence intervals will be presented. Participants who are missing both baseline and all treatment period values will be excluded. The missing at random assumption of MMRM will be utilized, and no imputation will be performed for missing observations.

The summary and analyses of the non-PK exploratory endpoints will also be performed using the PD evaluable population.

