1.3. Schedule of Events and Assessments

Table 1 provides the timing of the events and assessments to be conducted in this study. Also refer to the appropriate sections of this protocol and accompanying study manuals (eg, laboratory, pharmacy, imaging) for more information.

Table 1: Schedule of Events

Period →	Screening	Treatment					Follow-up
Study Day →	Day -60 to -4	Day 1	Day 15	Day 29	Day 58	Day 87/EoT ^a	Day 101
Allowable visit window (days) →			±2	±4	±4	±4	±4
Procedures ↓							
ICF signed	X						
Eligibility evaluation	X	X					
MMSE (see Section 9.2)	X	X ^b				X	
Demography	X						
Medical history	X	X					
Complete physical exam (see Section 9.4)	X						
Symptom-directed physical exam		X	X	X	X	X	X
Weight (W), height (H)	W, H	W	W	W	W	W	W
12-lead ECG ^c	X	X ^b	X	X	X	X	
Vital signs (RR, O ₂ , BP/pulse, including orthostatic) (see Section 9.6)	X	X	X	X	X	X	X
Urinalysis (UTI screening) ^d	X						
Blood sample (genetics; see Section 9.7.1)	X						
Blood sample (chemistry, coag/hematol, lipids)	X	X ^b	X	X	X	X	X
Blood sample (biomarkers)		X ^b	X	X	X	X	X
Blood sample (PK)			X	X	X	predose post: 2,4,6h (±15m) ^e	
C-SSRS (see Section 9.8)	X	All visits (including unscheduled)					
Participant diary (see Section 9.9)	Issued	Each visit: Monitored and filed as source document, new diary issued					Returned
Adverse event monitoring	X	X	X	X	X	X	X

Table 1: Schedule of Events (Continued)

Period →	Screening	Treatment					Follow-up
Study Day →	Day -60 to -4	Day 1	Day 15	Day 29	Day 58	Day 87/EoT ^a	Day 101
Allowable visit window (days) →			±2	±4	±4	±4	±4
Procedures ↓							
Prior & concomitant meds (see Sec. 8.7)	X	X	X	X	X	X	X
Cognitive battery (see Section 9.11)	X ^f	X ^b	X	X	X	X	X
EEG, ERP (see Section 9.12)	X	X ^b	predose, and at 2h (±30m) postdose				X
Neuroimaging (rs ASL, fMRI) (see Sec. 9.13)	X ^g	X ^b	4 (±1½) h post			4 (±1½) h post	
CSF sampling (biomarkers & PK)	X ^h					6h (±15m) post ^e	
Study drug dosing ⁱ , supply, accountability		X	X	X	X	X	

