Note: All assessments on dosing days are performed predose unless otherwise noted. Assessments for all scheduled study visits can be performed across multiple days **provided that:** the assessments occur within the stated visit window, the predose assessments are performed before the daily dose is taken, and postdose assessments occur at the stated time per protocol. For example, the Day 15 visit assessments could be conducted across 2 days, such that on Day 14, all predose assessments could be completed prior to administration of the Day 14 dose, with the EEG performed at 2 hours postdose; and then on Day 15, the participant could undergo the MRI 4 hours after taking the Day 15 dose. Also see footnote b.

ABCA7=adenosine 5triphosphate (ATP)-binding cassette sub-family A, member 7; ApoE4=apolipoprotein E4; ASL=arterial spin labeling; BP=blood pressure; coag=coagulation; CSF=cerebral spinal fluid; C-SSRS=Columbia-Suicide Severity Rating Scale; ECG=electrocardiogram; EEG=electroencephalography; EoT=end of treatment; ERP=event-related potential; fMRI=functional magnetic resonance imaging; h=hour(s); H=height; hematol=hematology; ICF=informed consent form; m=minute(s); meds=medications; MMSE=Mini-Mental State Examination; O₂=oxygen saturation; PK=pharmacokinetic(s); post=postdose; pre=predose; RR=respiratory rate; rs=resting state; UTI=urinary tract infection; W=weight; X=predose

^a EoT visit assessments also to be conducted (if possible) for participants who prematurely discontinue from study drug. See Section 7.6.

^b If the Screening safety laboratory and ECG assessments are conducted within 1 week before Day 1 and the participant meets all eligibility requirements, the safety laboratory and ECG assessments do not need to be repeated on Day 1. In addition, the Day 1 predose MMSE, ECG, biomarker and safety laboratory sampling, cognitive battery, and the EEG, ERP, and neuroimaging can be conducted up to 3 days before Day 1.

^c ECGs should be obtained after the participant has rested supine for ≥5 minutes. When timing coincides, ECGs and vital signs can be assessed together, but ECGs and vital signs should be obtained before blood draws (or ≥10 m after a blood draw, if necessary). See Section 9.5.

^d Because of the potential for UTIs to cause sudden confusion or delirium, a urine sample will be tested for infection at Screening. Standard of care will be administered for a positive test result.

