6.3.2. Blinding/Unblinding and Data Review

This will be an investigator- and participant-blinded, sponsor-unblinded study. The following practices will apply:

- Sponsor review of unblinded data will facilitate decision making on project progress and potentially trigger plans for additional studies.
- A Sponsor Data Review Committee (DRC), which will consist of the sponsor program director, medical director, senior management (medical) representative, will review unblinded data at the aggregate level for decision-making purposes. The DRC will not have access to specific participant treatment assignments so as to limit potential bias in discussions with the study sites. The sponsor's biostatisticians and programmers will, however, have access to participants' randomization assignments for analysis purposes. The remaining members of the core sponsor study team and the entire contract research organization (CRO) study team will be blinded.
- The DRC charter will outline the specific individuals involved, the frequency and activities involved in this review, and measures taken to maintain the integrity of the study.

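### Does the EEG/ERP analysis lose something it should keep by adjusting only for the last predose session and not also for Screening?

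*Combined protocol and SAP*

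**What the plan says.** Table 1 (Section 1.3) lists EEG/ERP at Screening (Day -60 to -4), on Day 1, at the later treatment visits (predose and 2 hours postdose) and at Follow-up. Footnote b says that "the safety laboratory and ECG assessments do not need to be repeated on Day 1" when Screening falls close enough to Day 1. That waiver does not cover EEG. The same footnote says that "EEG, ERP, and neuroimaging can be conducted up to 3 days before Day 1", so the Day 1 session may move earlier but is still done. Two pre-treatment EEG/ERP sessions are therefore planned for everyone.

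Section 10.4.3 defines baseline as "defined as the last non-missing assessment prior to the first administration of study drug, usually the predose assessment on Day 1". The MMRM for change from baseline takes "the respective baseline value as the covariate". Treatment differences are "estimated for the overall treatment period and at each assessment timepoint", with 90% confidence intervals, and "no imputation will be performed for missing observations". Section 5 names change to Day 87 as the qEEG/ERP endpoint and classes it as exploratory. Section 10.1 treats all p-values as nominal, and Section 10.4 leaves technical detail to the SAP.

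**The concern.** With about 30 participants, the intervals for the EEG/ERP treatment differences will be wide. A pre-treatment value that predicts the outcome removes between-person variation, and two such values often remove more than one. The Screening session is already scheduled and costs nothing further to collect, yet the model uses it only when Day 1 is missing. It seems that one extra covariate would give a narrower interval without new data. If so, the sponsor would be judging a pharmacodynamic signal with less precision than its own data allow.

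**Working it through.** **Is the planned estimate valid?** Screening and Day 1 values both precede treatment, and assignment is randomized. Leaving one out cannot bias the treatment difference. In simulation (6,000 trials per scenario, 30 participants), type I error was between 0.095 and 0.104 with one or two covariates, against the nominal 0.10. Only precision is in question.

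**Inputs.** About 30 participants randomized 1:1 (Sections 6.2 and 6.3.1), taken as 15 per arm; 90% intervals (Section 10.4.3). Section 10.2 sets the sample size outside statistical considerations, so there is no planned power figure to reproduce. The documents give no EEG variance or between-session correlation; every correlation below is assumed.

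**Formula.** An ANCOVA at Day 87 (m = 1), or on the mean of the four later treatment visits (m = 4), stands in for the MMRM. Each visit counts as one value with unit variance. Correlations are d (Day 1 with post), s (Screening with post), q (Screening with Day 1) and p (post with post).

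- v = (1 + (m-1)p)/m
- Residual variance, Day 1 only: v1 = v - d²
- Residual variance, both sessions: v2 = v1 - (s - qd)²/(1 - q²)
- Interval-width ratio = √[v2(1 + 2/25) / (v1(1 + 1/26))] × t(0.95; 26 df)/t(0.95; 27 df)

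**If Screening adds nothing (v2 = v1).** √(1.0800/1.0385) × 1.7056/1.7033 = 1.021, so 2% wider. To break even, the partial correlation of Screening with the outcome given Day 1 must reach √(1 - 1/1.021²), about 0.20.

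**All correlations equal.** At 0.7 and m = 1, v1 = 1 - 0.49 = 0.51 and v2 = 0.51 - (0.70 - 0.49)²/0.51 = 0.4235, which gives 0.931.

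| Common correlation | Day 87 | Four-visit mean |
|---|---|---|
| 0.5 | 0.963 | 0.901 |
| 0.7 | 0.931 | 0.852 |
| 0.9 | 0.899 | 0.810 |

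This case requires a session up to 60 days before Day 1 to predict Day 87 as well as Day 1 does.

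**Screening predicts no better than Day 1, often worse.** With d = 0.7, the Day 87 ratios are:

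| | s = 0.70 | s = 0.65 | s = 0.60 |
|---|---|---|---|
| q = 0.7 | 0.931 | 0.970 | 0.997 |
| q = 0.8 | 0.965 | 0.998 | 1.017 |
| q = 0.9 | 0.995 | 1.019 | 1.016 |

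The lower rows matter because the two pre-treatment sessions can be as little as one day apart (Day -4 and Day -3) and may then resemble each other more than either resembles Day 87.

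**Correlation that fades over the visit days.** Let two sessions g days apart correlate at R[w + (1 - w)exp(-g/τ)], where w is a stable personal share, τ a decay constant and R a reliability. Day 1 to Day 87 is 86 days. Example: w = 0.5, τ = 60 days, R = 0.8, Screening 30 days before Day 1. Then q = 0.643, d = 0.495 and s = 0.458; v1 = 0.755 and v2 = 0.721; the ratio is 0.998, which is no practical change.

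The grid was w = 0.3, 0.5, 0.7, 0.8; τ = 30, 60, 120 days; R = 0.7, 0.8, 0.9, 0.95; gap 7, 30, 60 days (144 combinations):

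| | Narrowest | Median | Widest | Share narrower |
|---|---|---|---|---|
| Day 87 | 0.938 | 0.992 | 1.017 | 64% |
| Four-visit mean | 0.889 | 0.963 | 1.012 | 89% |

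The shares describe this grid and are not probabilities.

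**Missing sessions.** A second covariate needs a rule for a missing Screening value. If Screening adds nothing and participants without it are dropped, losing 1 or 2 of 30 makes the Day 87 interval 4% or 6% wider. Filling in a mean keeps the loss at 2%, but that is an imputation.

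**The case for a change.** The best case for adding Screening is the asymmetry. With complete data or a fill rule, the expected loss is about 2% at most. The possible gain is about 10% at Day 87 and 19% for the overall period. At equal correlations of 0.5 to 0.8, the Day 87 gain is worth having about 32 to 36 participants instead of 30. The sample size was never set for precision, the data are already scheduled, and sponsor review feeds project decisions. If the model were ever to be extended, it should be settled early, because the sponsor's biostatisticians have access to participants' "randomization assignments for analysis purposes".

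The facts and arithmetic in that case stand, and so does the point about timing. The expectation of a useful gain at the named endpoint does not. The largest figures need undiminished correlation over up to five months. The firmer gain is for the overall-period estimate, which is not the Section 5 endpoint. Its four-visit stand-in also simplifies a schedule with predose and postdose recordings. Even at equal correlation of 0.5, the interval was narrower in only 66% of single simulated trials; when Screening adds nothing beyond Day 1, in 21%.

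Nor is the Screening session wasted. It is the fallback baseline, Section 10.4.3 summarizes results at each assessment timepoint, and it can inform Exclusion Criterion 9 on tolerating the EEG procedure.

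**Conclusion.** The concern does not hold. The schedule and the model are read correctly, but the planned analysis is conventional, unbiased and adequate for an exploratory endpoint with nominal p-values. No stated objective depends on a second baseline covariate.

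At Day 87 the effect of adding one runs from about 10% narrower (all correlations equal at 0.9) to about 2% wider (Screening uninformative given Day 1). It is close to nil at the middle of the fading-correlation grid. Even its sign rests on correlations that the documents do not supply. The price would be a fill rule, an exception to the no-imputation statement, a model that differs from those for the other pharmacodynamic endpoints, and more output for each EEG/ERP parameter if the planned model is also reported. Reasonable statisticians could choose either way, and the plan needs no change. The figures assume 15 per arm and an ANCOVA in place of the MMRM and, except for the missing-session figures, complete data.

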5. OBJECTIVES AND ENDPOINTS

Objective	Endpoints
Primary (Safety): 
• To evaluate the safety and tolerability of CY6463 when administered to participants with ADv	
• Incidence of TEAEs from study drug initiation through Follow-up
Exploratory (Pharmacokinetics): 
• To evaluate the PK of CY6463 when administered to participants with ADv	
• Plasma and CSF concentrations of CY6463 at assessed timepoints• PK parameters as data permit, including but not limited to T_{max}, C_{max}, C_{trough}, and the CSF:plasma concentration ratio
Exploratory (Pharmacodynamics): 
• To evaluate the effect of CY6463 on brain neurophysiology in participants with ADv• To evaluate the effect of CY6463 on CBF in participants with ADv• To evaluate the effect of CY6463 on brain activity in participants with ADv• To evaluate the effect of CY6463 on brain small-vessel pathology in participants with ADv• To evaluate the effect of CY6463 on biomarkers in participants with ADv• To evaluate the effect of CY6463 on cognitive performance in participants with ADv	
• Change from baseline to Day 87 in qEEG and ERP parameters• Change from baseline in CBF on Day 87 as measured by ASL• Change from baseline on Day 87 in fMRI BOLD signal• Change from baseline in white matter structural integrity on Day 87 as measured by MRI• Change from baseline on Day 87 in CSF and plasma biomarkers levels• Change from baseline on Day 87 in cognitive performance assessments• Change from baseline on Day 87 in MMSE score

ADv=Alzheimer's disease with vascular pathology; ASL=arterial spin labeling; BOLD=blood-oxygen-level-dependent; CBF=cerebral blood flow; C_{max} =maximum observed plasma concentration; CSF=cerebral spinal fluid; C_{trough} =trough plasma concentration observed at the end of a dosing interval [collected before the next administration]; ERP=event-related potential; fMRI=functional magnetic resonance imaging; MMSE=Mini-Mental State Examination; MRI=magnetic resonance imaging; PK=pharmacokinetic(s); qEEG=quantitative electroencephalography; TEAE=treatment-emergent adverse event; T_{max} =time to C_{max}

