9.12. Neurophysiological Assessments

Details of EEG procedures will be described outside of this study protocol. Because the postdose EEG assessment will be approximately 2 hours after the predose EEG assessment, the electrodes should remain in place to reduce variability and ensure consistent testing conditions.

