10.4. Statistical Analyses

This section summarizes the planned statistical analyses of the endpoints listed in Section 5. A more detailed and technical description of these analyses will be included in the statistical analysis plan (SAP).

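### Does the visit-only MMRM break down for EEG/ERP, which is recorded twice at each treatment visit?

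*Combined protocol and SAP*

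**What the plan says.** Section 10.4.3 sets out a single MMRM with "treatment, visit, and treatment-by-visit interaction as fixed effects and the respective baseline value as the covariate with unstructured as the variance-covariance structure". It goes on: "Treatment differences between the CY6463 group and the placebo group will be estimated for the overall treatment period and at each assessment timepoint". Baseline is one value per participant, the last one available before the first dose, "usually the predose assessment on Day 1".

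In Table 1 (Section 1.3) the treatment-period entry for EEG and ERP is "predose, and at 2h (±30m) postdose", with single recordings at Screening, Day 1 and Follow-up. Section 9.12 confirms the pair: "Because the postdose EEG assessment will be approximately 2 hours after the predose EEG assessment", the electrodes stay on. The endpoint in Section 5 is "Change from baseline to Day 87 in qEEG and ERP parameters", with no mention of predose or postdose.

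Three other places bear on the point. Section 10.1 makes the exploratory tests two-sided at 10%, unadjusted, with nominal p-values. Section 10.4 leaves the technical description to the SAP; the text available for this check contains no separate SAP chapter. Section 6.3.2 says of the sponsor's staff that "biostatisticians and programmers will, however, have access to participants' randomization assignments for analysis purposes".

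**The concern.** Visit is the only time factor in the model, yet EEG/ERP yields two values per visit. An unstructured covariance indexed by visit has no entry that distinguishes two recordings made on the same day, and treatment-by-visit gives one contrast per visit where EEG/ERP has two timepoints. Read as one joint fit, the stated model fails, and the analyst would have to choose a replacement: use one recording, average the two, or add a within-visit time factor.

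These options estimate different things. The predose recording shows the effect at the end of a dosing interval; the later one shows it 2 hours after a dose. An average, or an overall effect taken across both, mixes them. Section 5 leaves open which Day 87 value answers the endpoint. Because the sponsor's statisticians hold the treatment codes, a choice left open could be made with results in view.

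**Working it through.** **Inputs.** Two recordings per treatment visit (Table 1, Section 9.12). About 30 participants, 1:1, so about 15 per arm (Sections 6.2 and 6.3.1). Tests at two-sided 10% with 90% intervals (Sections 10.1 and 10.4.3), which agree with each other. The plan gives no power figure, effect size or SD, so there is no figure of its own to reproduce.

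The text as extracted does not show how far the EEG/ERP cell of Table 1 extends. I read it as covering Days 15, 29, 58 and 87: the note to Table 1 describes a 2-hour postdose EEG for the Day 15 visit, and Section 5 needs EEG on Day 87. That gives 4 × 2 = 8 on-treatment recordings.

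**1. All recordings in one fit, indexed by visit.** Let G be the 4 × 4 visit covariance and Z the 8 × 4 matrix assigning recordings to visits. The implied covariance is ZGZ′, with rank at most 4. Two recordings at visit j have correlation g_jj / √(g_jj × g_jj) = 1. A numerical check gave rank 4 and a smallest eigenvalue of zero to rounding error. This fit cannot be done, and it fails openly: a singular covariance has no likelihood to maximise, so it cannot quietly return a wrong estimate.

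**2. The stated model, once per recording.** With k = 4 visits, the covariance has k(k+1)/2 = 10 parameters and the mean has 2k + 1 = 9 (intercept, treatment, 3 visit, 3 interaction, baseline). No term is added or dropped, and baseline stays as defined. The two fits give 4 + 4 = 8 contrasts, matching the 8 on-treatment recording times. Each fit also gives its own overall treatment-period estimate.

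**3. One fit indexed by visit and recording time.** With k = 8 there are 8 × 9 / 2 = 36 covariance parameters and 2 × 8 + 1 = 17 mean parameters. In simulation with 30 participants, assumed dropout of 0 to 30% and assumed correlation 0.5, both k = 4 and k = 8 converged to a positive-definite covariance in 200 of 200 runs per setting. A second simulation used 600 runs, 15 per arm, assumed correlation 0.85 within and 0.6 between visits, 15% dropout and 5% intermittent missing data. Coverage of the 90% interval for Day 87 at 2 hours was 87.5% (k = 8) and 88.8% (k = 4). The Monte Carlo standard error was about 1.3 points, so no difference is shown. This route is heavier but workable.

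**4. Mixing the two effects.** Only in route 3, or if recordings are averaged, is the overall estimate half the mean predose difference plus half the mean 2-hour difference. If the predose effect is a fraction r of the 2-hour effect, the share shown is (1 + r)/2: 0.50 at r = 0, 0.75 at r = 0.5, 0.85 at r = 0.7. The values of r are assumptions. Estimates for individual timepoints are not affected.

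**5. Choosing between two Day 87 recordings.** Under no effect, the chance that at least one of two 10% tests is nominally significant is 1 − 0.9² = 19.0% if they are independent. By the bivariate normal it is 17.6% at correlation 0.5, 16.1% at 0.7 and 13.6% at 0.9 (correlations assumed), against 10% for one recording named beforehand.

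**The case for a change.** The best argument for amending is that the separate-fit reading is nowhere written down. Section 10.4.3 promises an effect over the whole treatment period; separate fits give two such effects and a joint fit gives one blended one, and the section does not choose. Section 5 is where endpoints are defined, and no choice of model tells the reader which Day 87 recording is meant. With treatment codes open to the sponsor's statisticians and unblinded aggregate data feeding project decisions (Section 6.3.2), writing the choice down beforehand costs one sentence.

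The gap is real, and such a sentence in the SAP would be good practice. The claim that the analysis as written is impossible does not stand: it needs a stacked fit that the plan never describes. The claim of a distorted result does not stand either. The dilution in step 4 depends on an effect ratio the documents do not give and on a pooling they do not prescribe. The inflation in step 5 requires that one recording be suppressed, whereas Section 10.4.3 provides summaries and treatment differences at each timepoint, so a reader would see both. Section 5 also names an open class of qEEG and ERP parameters with no single lead variable, so naming a recording would still not reduce it to one test.

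**Conclusion.** No change follows. This is missing detail that a competent analyst fills sensibly: the Section 10.4.3 model run separately on predose and 2-hour recordings is feasible at this sample size, uses exactly the stated terms, and gives a contrast at each on-treatment recording time. The one reading that fails, rank 4 for 8 recordings, fails visibly and leads back to the same solution.

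The remaining ambiguity is which Day 87 recording to put first. At worst it moves a nominal error rate from 10% to 19.0% per parameter, and only under selective reporting. Exploratory p-values are already declared nominal and unadjusted, no confirmatory claim depends on them, and the primary analysis of TEAE incidence is untouched.

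The conclusion rests on reading the EEG/ERP entry in Table 1 as covering all four treatment visits after Day 1, and on both recordings being reported as Section 10.4.3 provides. The SAP may already state the choice; the conclusion does not depend on it.
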